## Abstract

The fifth edition of the Diagnostic and Statistical Manual for Mental Disorders (DSM-5) introduces Internet gaming disorder (IGD) as a Substance-Related and Addictive Disorder in Section 3, Conditions for Further Study. Although research is in the nascent stages, existing studies demonstrate that IGD is associated with psychosocial distress including suicidality, and adverse vocational and educational outcomes in youth. Internet gaming disorder also shares substantial overlap with substance use, and it primarily affects adolescents, who rarely seek treatment on their own. Parents more often express concerns about their child's game playing behaviors, and data suggest that parents can have strong influences on it. This psychotherapy development study will evaluate feasibility, acceptability, and effect sizes of a behavioral intervention designed to help parents reduce gaming problems in their children. Sixty concerned parents and their children will complete parental and self-report inventories and structured diagnostic interviews regarding the child's gaming behaviors, substance use and psychosocial functioning. Participants will be randomized to either a control condition consisting of referral for mental health issues and family support services or to the same plus a 6-week family-based behavioral intervention designed to assist with better monitoring and regulating the child's game playing behaviors and encouraging and rewarding alternatives to game playing. Gaming and other problems will be assessed pre-treatment, mid-treatment, at the end of treatment, and at a 4-month follow-up. This study is unique in evaluating initial psychometric properties of a parental version of a measure that uses the DSM-5 criteria for IGD in a clinical sample, and it will also assess associations of IGD with substance use, psychological symptoms, and family functioning over time. Most importantly, this study will be the first randomized trial of an intervention designed to reduce gaming problems, and results are likely to guide future research and treatment efforts related to this condition.

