### Approach

**Subjects** will be recruited by ads directed at parents, e.g., "Has your child developed problems from playing video games too much?" Staff will inform callers that the study involves both parent and child participation.

Inclusion criteria are: (1) parent/guardian of a 10-19 year old residing in the same household  $\geq 8$  months/year; and (2) child meets DSM-5 IGD criteria by self-report or by parent report (see below and Human Subjects).

Exclusion criteria are parent or child has a significant other mental health condition that may impact response to treatment (active suicidality, psychosis), and parent or child is unable to attend 6 sessions over 8 weeks.

Child age range spans early to late adolescence, and residential criteria ensure the child lives primarily with the target parent (allowing for visitation of divorced parents, but not boarding students). The child must meet DSM-5 IGD criteria via the self-reported or parent-reported VGDS or semi-structured interview. The self-report version of the VGDS has established psychometric properties (Rehbein et al., 2015) and we have found evidence of validity of the parent-version of the VGDS in our current pilot study, as evidence by concordance between the parent VGDS and a clinical interview administered by doctoral level clinicians.

**Informed consent.** Persons who call and appear eligible will be invited to an in-person assessment, at which we will obtain written informed consent from parents and children aged 18 years; those  $< 18$  will provide assent.

**Assessments.** Staff will administer instruments with established psychometric properties (when available) to assess study entry criteria, hypothesized mechanisms of action, and outcomes. Most measures will be collected at baseline (BL), week 4, post-treatment, and a week 24 follow-up. There are some exceptions. The demographic interview will be administered at BL only. The AUDIT, DUDIT, BRIEF, BIS-11 (parent and child versions), SRS, and the DERS will be administered at BL and post-treatment only. The SCID, TLFB, and the T-ASI will be administered at BL, post-treatment, and week 24 only. Abbreviated versions of some measures will be administered at the follow-ups. Some variability in the scheduling of the follow-ups will be allowed to account for variability between families in how quickly they complete the 6 sessions of therapy.

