- Social Phobia and Anxiety Inventory for Children (Beidel et al., 1995);
- Center for Epidemiological Studies-Depressed Mood scale (Radloff, 1977);
- Pittsburgh Sleep Quality Index (Buysse et al., 1989).
- the Youth Self-Report (Achenbach, 1991) of emotional and behavioral problems,

- DERS (Gratz & Roemer, 2004),
- quality of life KINDL-adolescent version (Ravens-Sieberer, 2000)
- the adolescent version of the Barrett Impulsiveness Scale (BIS-11), a measure of their own impulsivity (Patton, Stanford, & Barratt, 1995)

**Randomization.** After baseline, families will be randomized via a computerized algorithm (Stout et al., 1994) to groups below. Groups will be stratified by child age ( $\leq 15$  or over), sex, and parents participating (one vs. both).

**A. Referral for care.** Therapists will explain that gaming problems often co-occur with other mental health problems, and effective treatment for the latter may reduce gaming as well. Therapists will refer parents to local support groups such as Department of Mental Health and Addiction Services and National Association for Mental Illness support groups. Adolescents will be referred for appropriate services as well, e.g., depression, social anxiety, ADHD, or substance use depending on co-occurring problems.

**B. Referral plus Behavioral therapy** will consist of referral for other services plus 6 family sessions (adapted from Petry, unpublished; Appendix). In Session 1, therapists will review baseline information, refer for other services, and orient participants to treatment. They will remind parents that although they cannot prevent playing entirely, they can better understand why and when their child is playing and alter their reactions toward it, which may decrease the extent of play and problems. Therapists will describe methods to re-arrange the home to better monitor and be less conducive toward playing; this may include altering locations of or removing some (or all) gaming devices from the home. Therapists will review a tracking form and instruct parents how to and benefits of closely monitoring their child's playing. Children will be asked to keep their own log as well.

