Session 2 will focus on goal setting for gaming, ranging from 0 to  $\leq 12$  hrs/week (Council on Communications and Media, 2013). It will begin with a review of past weeks' logs. Therapists will troubleshoot difficulties with monitoring and concordance of child and parent logs. They will review patterns of play to identify high-risk times and days, and circumstances that may have impacted playing. Therapists will outline norms related to game playing and media use in general to guide selection and maintenance of reasonable goals.

In session 3, therapists will review logs and how actual gaming aligned or not with goals. Therapists will also introduce the concept of replacing high-risk game playing times with alternate activities. The parent, and child, will review a list of recreational activities the child does or may enjoy. At least 2-3 activities will be identified to occur at high risk gaming times in the upcoming week. Over the next week, participants will continue recording gaming and times in which parents encouraged alternate activities and the child's responses.

Session 4 will review goals in light of increasing alternate activities, and therapists will introduce the concept of rewarding non-game playing behaviors this session. They will outline possible rewards, and parents will develop a concrete plan to reward their child for not playing during high-risk times in the next week.

Session 5 will continue discussions of rewards for non-gaming playing behaviors. Therapists will review rewards provided and encourage continued rewarding of non-game playing and other positive behaviors in the future. The session will focus on communication styles, and the parent and child will role play assertive communication skills, especially as they relate to game playing.

Session 6 will review progress and discuss long-term goals. Therapists will remind parents to continue to monitor play, offer alternatives to play, and reward non-gaming behaviors to prevent relapse. The therapist will help parents to problem solve any barriers to successful implementation of the behavior plan.

Six sessions will be scheduled about once per week over 8 weeks, allowing for missed or re-scheduled sessions. The goal will be to complete 6 sessions over 8 weeks; no reschedules will occur after week 12. Sessions may be completed over the phone if needed.

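### The post-treatment gaming assessment has no fixed week and may follow therapy completion, which only Group B has, so its timing can differ by arm

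*Combined protocol and SAP*

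**What the plan says.** The Assessments paragraph of the Approach section gives the visit schedule: "Most measures will be collected at baseline (BL), week 4, post-treatment, and a week 24 follow-up". For the gaming outcome it is narrower: "The SCID, TLFB, and the T-ASI will be administered at BL, post-treatment, and week 24 only". The TLFB is thus not collected at week 4, and post-treatment is its first measurement after baseline. The same paragraph then lets visits move: "Some variability in the scheduling of the follow-ups will be allowed to account for variability between families in how quickly they complete" the six sessions. No limit on that variability is given.

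The arms differ in what could move a visit. Under the description of the two conditions, Group B "will consist of referral for other services plus 6 family sessions". Group A is referral: "Therapists will refer parents to local support groups such as Department of Mental Health and Addiction Services", with referral of the adolescent to other services as needed. It has no session series and so no completion date. For Group B the session plan reads: "The goal will be to complete 6 sessions over 8 weeks; no reschedules will occur after week 12".

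The final visit is week 24 in the Assessments paragraph. The Abstract instead says assessment will be "at a 4-month follow-up", and the Specific aims place it four months after the other evaluations.

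The Data analysis section (Aim 2) and section 10 of the Data and Safety Monitoring Plan specify an HLM with group, time and their interaction. Effects are evaluated over baseline to post-treatment and over the longer term. Neither section defines time as nominal visit or as elapsed days.

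**The concern.** A randomised comparison of change over time needs the outcome measured at the same distance from randomisation in both arms. Here a stated rule ties visit dates to something that exists in one arm only, and nothing else in the plan restores the balance.

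Three consequences follow if the rule is applied as written:

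- Group B families who take longer over their sessions can be assessed later, while no rule says when a Group A family has its post-treatment visit.
- Timing in Group B then depends on adherence, and slow families are unlikely to be a random subset.
- If gaming falls over time whatever the treatment, extra time before assessment in Group B looks like benefit.

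A common fall is plausible. Families enter because of current concern, and the Background describes a randomised trial of group therapy against no treatment in which Internet use fell similarly in both groups. That trial concerned Internet use in general, and the protocol gives no rate of change from it.

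The effect estimate is a main product of this pilot: a medium or larger effect is part of the stated basis for proposing a larger trial.

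**Working it through.** **The plan's own figure.** The Power analyses paragraph gives 30 per group, d = 0.65, alpha .05 and power .80. With a t test on 58 degrees of freedom and noncentrality 0.65 × √15, power is 0.800 one-sided and 0.697 two-sided. The figure reproduces only as a one-sided test, and sidedness is not stated. That is a separate matter; 0.65 serves here only as a yardstick.

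**How far timing can spread.** Assume week numbers count from randomisation; the documents do not state the origin. Six sessions at about one per week end near week 6 at the earliest. The goal is week 8 and the outer limit week 12. The spread in Group B is up to 12 − 6 = 6 weeks. Group A generates no such spread.

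**Size of the bias.** If the model uses nominal visit as time, and both arms share a linear drift,

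bias (SD) = drift per week × mean lag between arms.

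Neither input is in the documents. The ranges below are assumptions.

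| Drift (SD/week) | Mean lag 1 wk | 2 wk | 4 wk | 6 wk |
|---|---|---|---|---|
| 0.01 | 0.01 | 0.02 | 0.04 | 0.06 |
| 0.02 | 0.02 | 0.04 | 0.08 | 0.12 |
| 0.05 | 0.05 | 0.10 | 0.20 | 0.30 |

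As a share of 0.65, this runs from 0.01/0.65 = 2% to 0.30/0.65 = 46%. Two-sided type I error with 30 per arm (noncentrality = bias × √15) is 0.051 at a bias of 0.02, 0.053 at 0.04, 0.119 at 0.20 and 0.208 at 0.30.

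**Which part of the table is likely.** The lag that matters is the difference in arm means, not the delay of the slowest families. As an illustration, suppose controls are seen at week 8, a quarter of Group B at week 12 and the rest at week 8. The mean lag is 0.25 × 4 = 1 week, and the bias is 0.01 to 0.05 SD. A mean lag of 6 weeks needs every Group B family seen at week 12 and every control at week 6.

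**The final visit.** Four months is 4 × (365.25/12)/7 = 17.4 weeks.

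| Sessions end | Week 24 falls after last session by | Four months after last session falls at |
|---|---|---|
| Week 6 | 18 weeks | week 23.4 |
| Week 8 | 16 weeks | week 25.4 |
| Week 12 | 12 weeks | week 29.4 |

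Held at week 24, the visit has equal time since randomisation in both arms and the mechanism above adds no bias. Only if it were moved to four months after therapy could its timing differ by arm.

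**The case against.** The strongest reply is that the documents permit different timing but do not prescribe it. They are silent on when Group A has its post-treatment visit, and staff could use a common week or match controls to Group B. The Approach section also allows general flexibility for missed and late appointments, not limited to one arm. A reader might infer that the arms are in fact measured at different times; the text does not support that. It does contain a rule that is asymmetric when followed, with nothing to offset it.

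A reader might also infer a comparable bias at the last visit. That visit is nominally week 24 in both arms. The varying gap since the last session is a different quantity, and fixed weeks from randomisation would produce it too. Week 24 and four months also roughly agree for a family finishing at week 8 (16 against 17.4 weeks). What stands is smaller: the flexibility sentence covers the follow-ups generally, and the two descriptions of the visit leave its origin open.

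Third, a reader might multiply drift by the 4 to 6 weeks that the slowest families could add and set the product against 0.65. That compares some families' delay with a difference in arm means. The 8-week goal, and the exclusion of families unable to attend six sessions in 8 weeks, point to a short mean lag.

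Finally, the HLM could use elapsed time, and TLFB data are recorded by day, so alignment by date may be possible. Neither is specified, and the TLFB window is not stated. Assessing Group B after therapy ends is also a defensible choice in a Stage 1 pilot, but it then needs a matching rule for Group A.

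**Conclusion.** The concern holds for the post-treatment gaming outcome, as a gap that allows bias rather than a demonstrated bias. Its timing can differ by arm and follow adherence in Group B, and the plan neither prevents this nor adjusts for it.

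The size cannot be fixed from the documents. It is about 0.01 to 0.30 SD under the assumed drift and mean lag, with nominal visit as time and linear drift. The low end is more likely given the 8-week goal. With no drift, or no mean lag, this bias is zero. Its direction favours Group B only if gaming falls over time and Group B is seen later.

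For the final visit the concern is weaker and is mainly one of wording. This is a cheap improvement, not a flaw that undermines the trial.

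**What to change.** - Set the post-treatment and week-24 assessments at the same number of weeks after randomisation in both arms, with one common window, whether or not sessions are finished. Replace the sentence that ties follow-up dates to the pace of therapy.
- State the origin of the week count, and reconcile the four-month wording with week 24.
- Record the actual date of every assessment and report its distribution by arm.
- State how time enters the HLM, and add a sensitivity HLM using actual days since randomisation. This supports the common schedule but does not replace it: if visit dates depend on adherence, modelling elapsed time need not remove all of the bias.

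The cost is protocol wording and one extra analysis. Sample size, power and therapy are unchanged. The downside is that some Group B families will be assessed before their last session, or some weeks after it, so the visit measures status at a fixed time rather than at therapy completion.

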Both parents may participate and will complete the parental assessments (est. 2 hours), and both (when available) can participate in the therapy, consistent with how family therapy is typically provided. Both parents and children will complete a therapy satisfaction form post treatment. Children and parents will receive \$30 in gift cards for completing the baseline assessment and the 4 week follow-up and \$50 in gift cards for the post-treatment and 24 week follow-up interviews (up to \$160/family member).

Family members may complete their follow-up measures through the survey function of REDCap in advance of their in-person meetings. When the research assistant calls to schedule the follow-ups, participants will be given the option of receiving the survey link through e-mail, receiving a paper copy of the assessments by mail, or completing the measures when they arrive for their in-person meeting. The week 4 assessment can be completed in its entirety by the participant at home through REDCap or the mail, unless the participant prefers an in-person meeting. Study visits may be completed over the phone if needed.

Parents will provide:

- basic demographics, including age, SES, gender, and education of parents and child, and indices of the child's school functioning: grades, tardiness, absences and disciplinary issues

- modified Treatment Service Review (TSR; McLellan et al., 1992) questionnaire about histories and current treatments received (of the child). Additional questions specific to treatment for video game addiction treatment will be administered at all time points.
- Parents will provide data about their own psychological symptoms (Brief Symptom Inventory [BSI]; Derogatis, 1992)
- emotional regulation (Difficulties in Emotion Regulation Scale [DERS]; Gratz & Roemer, 2004).
- Parents' perceptions of their child's gaming will be evaluated by a revised VGDS (Rehbein et al., 2015), which includes items about types and locations of all gaming devices in the home and frequencies with which they monitor their child's gaming behaviors.
- a semi-structured clinical interview using DSM-5 criteria (SCID; Petry et al., 2014), assessed over past year and past 2 months at BL and past 2 months at other time points.
- Parents will complete a TimeLine Follow-Back (TLFB; Sobell & Sobell, 1990) of the child's gaming, time spent watching others play online (e.g., YouTube, Twitch), and sleep

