- iii. A trained and supervised doctoral level therapist will deliver the intervention. Discord or disagreements between children and parents will be addressed in therapy, and one full session of the treatment is devoted toward improving communication skills.
- iv. All data will be coded by number, not name, and a "key" form will be kept in a separate locked file cabinet. No information will be provided about the patients enrolled in this study to anyone outside of the clinical and research teams, except in emergency situations (e.g., patient deemed a threat to him/herself or others) or as required by law (e.g., child abuse/neglect). The study therapists are all doctoral level with substantial experience handling crises. If a therapist learns of potential abuse/neglect, they will notify the Connecticut Department of Children and Families (DCF) as required by law. If a therapist has concerns about potential suicidal or homicidal ideation, the therapist will conduct a comprehensive risk assessment and, if deemed necessary, the participant will be transported immediately to the emergency room for acute evaluation and treatment. Within the research context, research assistants may also hear indications of risk of harm to self or others or abuse/neglect. RAs will be well-trained on how to handle these situations. Specifically, the RA will immediately contact the PI, study coordinator, or study therapist who will assess safety and manage the crisis directly or instruct the RA on how to address risk, including (if necessary) arranging for transportation to an emergency room or reporting concerns about abuse or neglect to DCF.

Audio data will be collected digitally, will be stored on a password protected secure server, and destroyed at the end of the study; only research personnel will review the audio files for training, supervision, and adherence monitoring purposes. As noted earlier, an audiotaping section within the consent form will be used in the study, and patients may participate in the study without allowing audiotaping. All audio files will be labeled by number, not name, and the "key" form will be kept separate in a locked file cabinet.

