Finally, we will evaluate the psychometric properties of a semi-structured diagnostic interview based on the DSM-5 IGD criteria as well as the parent version of the VGDS. Briefly, internal reliabilities of symptoms and diagnostic criteria will be calculated using Cronbach's alpha. Parent and child reports on self-report and interviews will be compared using Shrout and Fleiss intraclass correlations for continuous variables and Kappa's for diagnostic assessments, with respect to endorsement of specific criteria and diagnosis. For both parent and child versions, we will also examine correlations with TLFB gaming behavior and other indices as we did previously (Rehbein et al., 2015) to determine convergent validity. Thus, this project allows for initial psychometric evaluation of a parent report measure and a structured clinical interview for IGD in youth.

**11. Quality assurance plan:** All research staff will be thoroughly trained and supervised regarding administration of interviews and completion of all necessary forms. Some measures will be entered directly into REDcap, an online data entry system that allows for direct input of data. REDCap allows for restriction of response values to insure that responses entered are valid and fall within the specified range. REDCap also prompts interviewers if responses are missing, thus greatly improving the accuracy of data collection. Finally, REDCap allows for direct download of complete data into a variety of software programs, including Excel and SPSS.

In addition, the project coordinator reviews at least 5% of the entered data for accuracy. Research assistants regularly audio-record their research interviews, and the project coordinator or other study staff listens to these recordings to insure accuracy of administration of interviews and recording of data in REDcap. If any specific variables are found to be consistently problematic, the project manager and research assistant will implement a specific training action plan to resolve the problem. The project manager is responsible for study documentation, including data correction and electronic data files. Prior to the conduct of the final analyses, the raw data will undergo extensive examination by the PI or project coordinator.

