**12. Reporting mechanisms of AEs/SAEs to the IRB, FDA, and NIDA.** Types of SAEs in this population are as follows: (a) onset of clinically significant suicidal ideation, intent or action; (b) onset of clinically significant homicidal ideation, intent or action; (c) deterioration of mental status to an extent that requires inpatient hospitalization or overnight stay at an acute treatment facility. All SAEs will result in the completion of an SAE Form within 48 hours to the Project Coordinator. Deaths and possibly study related SAEs will be reported immediately to the PI and within 72 business hours to the NIH project officer. We will follow our IRB's standard policy on reporting of SAEs, which is to report all serious, unexpected related to possibly related AEs to the IRB within 5 working days.

An Adverse Events Monitoring Form will be adapted from one being used in our ongoing trials. This form collects detailed information about all adverse events, how they were handled, and their potential relationship to study participation. The procedures for SAE reporting also include written documentation using the clinical notes related to the adverse event and specific forms detailing the event with a sign-off by appropriate supervisory personnel.

Other adverse events, such as suicidal ideation that does not require hospitalization, will also be recorded on an Adverse Events Monitoring Form. Clinically significant increases in gaming or other problems detected at follow-ups will result in referrals for further treatment.

An ongoing database of adverse events will be maintained by the study coordinator. About once per month, in research team meetings, all events that occurred in the previous month will be reviewed. In addition and according to university policy, the local IRB maintains records of adverse events, and records are sent to NIH per policy. Aggregate data on reports of adverse events are reviewed on at least an annual basis by the IRB for study continuation according to their established policies. Any temporary or permanent suspension of patient accrual will also be reported to NIH. We anticipate that unexpected and possibly study-related SAE's will be rare, because patients will be receiving a psychosocial intervention.

**13. Reporting mechanism of IRB actions to NIDA.** The PI will be responsible for informing NIDA of any actions taken by the Institutional Review Board as a result of its regular or special reviews of the project.

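### Only Group B has repeated clinician contact before post-treatment and no adverse-event question is scheduled in both arms, so suicidal ideation and other events are captured unequally

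*Combined protocol and SAP*

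**What the plan says.** **Contact after randomization** (Approach, Randomization, arms A and B). In Group A, "Therapists will explain that gaming problems often co-occur with other mental health problems, and effective treatment for the latter may reduce gaming as well", and they refer parents and adolescents to services. No later therapist contact is described. Group B "will consist of referral for other services plus 6 family sessions". These are roughly weekly over 8 weeks, with no rescheduling past week 12, in person or by phone.

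**Week 4** (Approach, Assessments). In both arms, "The week 4 assessment can be completed in its entirety by the participant at home through REDCap or the mail", unless the family prefers to come in. The interviews are not due then: "The SCID, TLFB, and the T-ASI will be administered at BL, post-treatment, and week 24 only". The child's "Center for Epidemiological Studies-Depressed Mood scale" and the Youth Self-Report are not among the stated exceptions, so by default they are collected at week 4, possibly abbreviated.

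**How risk comes to light** (Human Subjects 2.b.iv, repeated in section 17 of the Data and Safety Monitoring Plan). A therapist with concerns about suicidal or homicidal ideation does a risk assessment. In addition, "research assistants may also hear indications of risk of harm to self or others or abuse/neglect", in which case they contact the PI, coordinator or therapist at once.

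**What is counted** (Data and Safety Monitoring Plan). Section 12 lists among the SAEs "a) onset of clinically significant suicidal ideation, intent or action". It later places ideation managed without admission among other adverse events. It also says that clinically significant worsening found at follow-up leads to referral. Section 15 stops the trial if unexpected, possibly study-related SAEs reach 15% of the sample. On review of entered data, section 11 says that "the project coordinator reviews at least 5% of the entered data for accuracy", and adds a check of interview recordings and an examination of raw data before the final analyses.

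**The concern.** Events are recorded when someone on the study team notices them, and the chance of noticing depends on how often a clinician talks with the family. That frequency is set by the randomized arm.

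Two things are at stake. The first is safety. The background section links excessive gaming to suicidality, and youth with depression may enrol. A child in the referral arm could write down serious distress at week 4, and nothing in the plan says that anyone would read it before the post-treatment visit. The second is interpretation. Events missed in one arm lower the pooled count that feeds the monthly review (section 19) and the stopping rule, and any table of events by arm would partly measure contact rather than harm.

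**Working it through.** **Step 1: opportunities for detection between randomization and post-treatment.**

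| | Group A | Group B |
|---|---|---|
| Described therapist contacts | 1 | up to 6 |
| After the first contact | 1 − 1 = 0 | up to 6 − 1 = 5 |
| Week 4 | may be wholly at home | may be wholly at home |
| Interviews due at week 4 | none | none |
| Scheduled adverse-event or suicidality question | none described | none described |

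Session 1 in Group B includes the referral, so it is the counterpart of the single Group A contact. Research-assistant contact (scheduling and reminder calls) exists in both arms and is not counted here.

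**Step 2: what happens to an answer given at home.** The escalation route needs a therapist with concerns or an assistant who hears something. A web or posted form supplies neither. REDCap's checks cover value range and skipped items. The data reviews in section 11 are about accuracy and have no stated turnaround. The follow-up sentence in section 12 states what follows once a problem is found, but not how or when remote answers are examined.

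**Step 3: the plan's own threshold.** 0.15 × 60 = 9 affected, reading the study sample as 60 families with one index child each.

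**Step 4: illustration with assumed inputs.** Let *p* be the true risk, equal in both arms, and *s* the detection in Group A relative to Group B, with Group B detection set to 1. Neither value is in the documents. Setting Group B to 1 is generous, since it has no structured screen. Every event is assumed to count towards the stopping rule.

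- Expected recorded events: Group B 30*p*; Group A 30*ps*.
- Pooled recorded rate: *p*(1 + *s*)/2.
- True risk at which the recorded rate reaches 15%: 0.30/(1 + *s*).
- Chance of 9 or more recorded: exact, from the sum of Binomial(30, *p*) and Binomial(30, *ps*).

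| *s* | A vs B expected, *p* = 10% | True risk for a recorded 15% | P(9 or more), *p* = 15% |
|---|---|---|---|
| 0 | 0 vs 3.0 | 30% | 0.03 |
| 0.25 | 0.75 vs 3.0 | 24% | 0.10 |
| 0.5 | 1.5 vs 3.0 | 20% | 0.23 |
| 0.75 | 2.25 vs 3.0 | 17.1% | 0.39 |
| 1 | 3.0 vs 3.0 | 15% | 0.56 |

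Only the direction follows from the design. The rows show how it would act for a given *s*, and *s* = 1 removes the artificial difference.

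**The case against.** The case on the other side has real content.

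- *Group A also meets a therapist.* This stands. A reader might infer that clinicians see only Group B. The documents describe one therapist contact in Group A, so the difference is in repetition.
- *Group B has no screen either.* This stands. A reader might infer that ideation is found in Group B and missed in Group A. Group B has only more occasions for a therapist to become concerned.
- *Week 4 is not free of staff contact.* This stands in part. An assistant calls to schedule follow-ups, families may come in, the home option applies to both arms, and trained assistants escalate at once. But the call is described as a scheduling call, with no risk question.
- *Section 12 promises referral for problems found at follow-up, which presumes someone reads the answers.* This is a fair inference, and it means the 5% accuracy check should not be read as the only route by which answers are seen. It still leaves reader and timing unstated.
- *No between-arm safety analysis is planned.* This is correct. Safety is not a listed outcome, and section 20 rules out by-arm review of accumulating data. The bias therefore applies to any raw by-arm count someone might report. The possible undercount in pooled oversight does not depend on such a comparison, although only unexpected, possibly study-related SAEs count for stopping.
- *Active suicidality is an exclusion, the week 4 item set may be abbreviated, and the adverse-event form is not reproduced.* All true. The exclusion may lower the number of events but does not equalize their detection. The form may hold suitable questions, but nothing schedules its use at fixed times in both arms.
- *Unequal contact is inherent in adding sessions to referral, and an attention control was judged premature.* This is accepted. The point is not to equalize contact but to ask about events equally.

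**Conclusion.** The concern holds in this form: capture of adverse events and new suicidal ideation depends on contact, contact differs by arm (one described therapist contact against up to six), and no scheduled, arm-neutral question makes up the difference. In Group A an event can be missed or found late; the documents do not support saying that it will be. Pooled SAE counts may be too low. At equal true risk, a raw by-arm count would tend to show more events in Group B.

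The size cannot be derived. A reader might want a multiple, for instance that Group B would appear to have 1.3 to 3 times the events. That range comes from assuming 90% detection in Group B and 30% to 70% in Group A (0.9/0.7 = 1.3; 0.9/0.3 = 3.0), so it only restates the assumption. The stopping-rule figures above are conditional in the same way.

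Separately, section 12 draws two lines for suicidal ideation: clinical significance where it is an SAE, and need for hospitalization where it is another adverse event. Ideation that is clinically significant but managed without admission fits both. The sentences must be reconciled before any count is interpreted.

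**What to change.** 1. Ask the same short structured adverse-event questions at week 4, post-treatment and week 24 in both arms, whether the assessment is done in person, by phone, by REDCap or by mail.
2. State who looks at remote and mailed responses on receipt (a REDCap alert can support this), and pass them into the escalation route already described in Human Subjects 2.b.iv. This sets no new clinical rule.
3. Add a source field to the Adverse Events Monitoring Form: scheduled assessment or therapy session.
4. Base any between-arm safety statement on events from scheduled assessments, and list session-detected events separately.
5. Reconcile the two section 12 sentences on suicidal ideation.

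The cost is a few survey items, an alert or check on receipt, and one form field, using existing staff. The downside is slightly longer assessments and some false alerts.
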